2.0 PROTOCOL SUMMARY

2.1 Protocol Synopsis

Long Title	Double-blinded, placebo control, randomized, phase-3 clinical trial to evaluate clinical efficacy of Favipiravir in patients with mild to moderate symptoms related to COVID-19 infection
Short title	Favipiravir to shorten the time to sustained clinical recovery
Protocol No.	ATI0220
Version	5.1 dated 02-November-2021
Background	COVID-19 starts as a pure viral infection and evolves into a multifactorial disease with components of hyper immune activation, end organ damage, and fibrosis. Suppression of viral replication is expected to be impactful early in the course of disease. The ability to mitigate the symptoms at an early stage will prevent progression to severe COVID-19 and can save many lives. Early treatment could also reduce viral shedding, diminishing the period of infectivity and decreasing the number of secondary cases.
Study design	Double-blinded, placebo controlled, randomized, phase 3 trial evaluating the antiviral drug favipiravir as potential therapy for mild to moderate COVID-19 in adult outpatients who are not requiring hospitalization and who had a positive COVID-19 test within 72 hours of study enrollment. Mild to moderate symptoms are defined as: O ₂ Saturation \geq 94%, no requirement of supplemental O ₂ , lack of known sepsis or organ failure. Subjects will be randomly assigned to favipiravir (the first two doses are 1800 mg given approximately 12 hours apart, followed by 800mg approximately every 12 hours to complete 10 days of therapy) or placebo.
Favipiravir	A selective inhibitor of viral RNA-dependent RNA polymerase (RdRP) with potent antiviral activity against single-stranded RNA viruses including coronaviruses. It is indicated in the treatment of influenza in Japan and China and COVID-19 in Russia and India.
Sample size	The entire study: approximately 1250 (approximately 625 subjects per treatment arm) are estimated to be sufficient to get 815 sustained clinical recoveries. The viral shedding sub-study: approximately 550 (approximately 275 per arm) to obtain 112 viral shedding events.
Primary Study Objective	
 Demonstrate that treatment with favipiravir for COVID-19 patients with mild to moderate symptoms will shorten the time to sustained clinical recovery ('clinical endpoint component') compared to placebo.

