- Proportion of subjects with COVID-19 progression, defined as the occurrence from study day 1 onward of any ED visit for COVID worsening or shortness of breath **OR** hospitalization for COVID worsening or shortness of breath **OR** death **OR** the development of symptomatic worsening from study day 1 onward (defined as ≥ 2 additional COVID symptoms at a level of moderate or severe which have not existed at baseline or fever (temperature of $\geq 38.0^{\circ}\text{C}$) which has not existed at baseline or oxygen desaturation (O₂ saturation $<94\%$) which has not existed at baseline) (broad progression).

Viral Shedding Sub-Study:

- Time (number of days) to negative conversion (defined as undetectable viral load) of detectable SARS-CoV-2 viral RNA in RT-PCR assays of saliva, from start of study treatment to date of last viral assessment. Included: all subjects with a positive PCR on study day 1 or 2 or 3. The endpoint will be evaluated from study day 1 onward.

Additional Secondary Efficacy Endpoints

- Time (number of days) to negative conversion of positive SARS-CoV-2 viral culture assays of saliva, from start of study treatment to date of last viral assessment. Subjects with a positive saliva SARS-CoV-2 PCR on any study day will have viral cultures performed. Subjects with a positive viral culture on study day 1 or 2 or 3 will be included in this analysis. The endpoint will be evaluated from study day 1 onward.

Exploratory Endpoints (details of the planned analyses are described in SAP 3.1):

- Proportion of subjects showing sustained clinical recovery by study Day 1, 3, 5, 7, 10, 14, 21.
- Proportion of subjects showing resolution of Symptoms by Days 1, 3, 5, 7, 10, 14, 21, where resolution is defined as symptom severity of 0 for all symptoms as well as temperature of $<38.0^{\circ}\text{C}$ as well as oxygen saturation of $\geq 94\%$.
- Proportion of patients showing negative conversion of detectable SARS-CoV-2 viral RNA in saliva on study day 1 or 2 or 3 to undetectable viral load on Study Days 3, 5, 7, and 10. Included: all subjects with a positive PCR on study day 1 or 2 or 3.
- Proportion of patients showing negative conversion of positive SARS-CoV-2 viral culture in saliva on Study Days 3, 5, 7 and 10. Subjects with a positive saliva SARS-CoV-2 PCR on any study day

will have viral cultures performed. Subjects with a positive viral culture on day 1 or 2 or 3 will be included in this analysis.

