6.2 Exclusion Criteria

An individual who meets any of the following criteria will be excluded from participation in this study:

1. O₂ saturation <94%
2. Shortness of breath at rest
3. Heart rate \geq 125 per minute
4. COVID-19 symptoms first presented >5 days prior to randomization
5. Requirement for hospitalization at the time of enrollment
6. Participation in another trial or use of any experimental treatment for COVID-19
7. Treatment with high steroid dose i.e. >30 mg/day prednisolone equivalent (excluding stable chronic treatment) or remdesivir or anyone receiving SARS-CoV-2 monoclonal antibodies within 3 months prior to enrollment
8. Known sepsis or organ dysfunction/ failure
9. Known infection with a respiratory virus other than SARS-CoV2 (e.g. Influenza) or any known bacterial infection (affecting the respiratory system or any other system)
10. Inability to adhere to study requirements
11. For premenopausal women: unwilling or unable to use effective birth control measures
12. Known allergy to favipiravir
13. Known end-stage kidney disease or requiring hemodialysis or continuous ambulatory peritoneal dialysis (CAPD)
14. Known liver impairment greater than Child-Pugh A
15. Psychiatric illness that is not well controlled (defined as stable on a regimen for more than one year).

16. Known elevated uric acid levels in the past year or taking uric acid lowering medications (allopurinol, febuxostat)
17. History of hereditary xanthinuria or history of xanthine urolithiasis.
18. History of gout or actively being treated for gout.
19. Current use of the following medications, which cannot be discontinued for the duration of the study: pyrazinamide, hydralazine, more than 3000 mg of acetaminophen per day.

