7.1.2 Study Vital Signs Measurements and Health Information

- Oral Temperature: will be measured 2 times daily. It will be documented in the subjects' diary. Subjects will be allowed to take temperature lowering medications such as acetaminophen or NSAIDS.
- Heart rate: will be measured once daily and documented by the subject in the subject's diary.
- Oxygen Saturation: will be measured once daily and documented by the subject in the subject's diary. If the O₂ saturation result is 90-93%, the subject will repeat the measurement 2 hours later. If the result is <90%, the subject is instructed to contact the study team. The study team will decide if a recheck in 2 hours is appropriate or the subject needs further medical evaluation).
- Height and weight: Height and weight should be collected at the screening visit. In cases where this has not occurred at the screening visit, the date of collection will be recorded.

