- In-person clinical assessment will occur on study Day 1 as described in section 9.2.1 and on Day 10 as described in section 9.2.3. Remote patient visits will occur on study Day 3, 5, 7, and 9.
- Subjects to self-administer IP (Favipiravir/ Placebo) as per the instruction provided and report in diary twice daily. Site staff to assess IP adherence daily.
- Subjects to report Adverse Event and Concomitant Medications including OTC and herbal products daily.
- Site staff to assess Adverse Event and Concomitant Medications including OTC and herbal products daily
- Subject to collect oral temperature twice daily, and report in the diary.
- Subject to collect oximetry data once daily, with the caveat that if O₂ goes below 94%, an additional oximeter reading should be taken 2 hours later. If the daily O₂ saturation result is 90-93%, the subject will repeat the measurement 2 hours later. If the result is <90%, the subject is instructed to contact the study team. The study team will decide if a recheck in 2 hours is appropriate or the subject needs further medical evaluation)
- The patient's severity of COVID-19 associated symptoms will be evaluated and reported once daily, preferably at or around the same clock time, by the subject (for a period of 10 days or longer in case that the subject does not achieve the primary endpoint within the first 10 days). The study team will be reviewing the data reported by subject to ensure compliance, accuracy and completeness on days 1, 3, 5, 7, 9, 10, 14, 17, 21, 24, and 28.
- The subject will assess and score the severity of each COVID-19 associated symptom on a 4-point scale (for all symptoms besides vomiting and diarrhea: 0= none, 1= mild, 2=moderate, 3=severe. For vomiting and diarrhea: 0 = not at all, 1 = 1-2 times, 2 = 3-4 times, 3 = 5 or more times).
- Viral specimen (saliva) collection, storage and shipping (refer section 7.7 for more details).
- Refer "Schedule of Activities" table for additional information on activities and whether they are the responsibility of subjects and/or study team.

9.2.3 Treatment Day 10

In addition to procedures described in 9.2.2, the following procedures will be performed at the in-person follow-up visit on Day 10.

- Assess for AEs
- Review and assess COVID-19 signs and symptoms
- Document all current medications, including medications over the counter and herbal medications
- Document subject's status as an outpatient, subsequently hospitalized, or died

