9.2.4 Post Treatment Days (Day 14 to Day 28)

The following procedures will be performed at all follow-up visits (post-treatment days), expected to be done remotely, unless otherwise noted, on Day 14, 17, 21, 24, and 28:

- Assess for AEs
- Review and assess COVID-19 signs and symptoms
- Document all current medications, including medications over the counter and herbal medications
- Document subject's status as an outpatient, subsequently hospitalized, or died
- Perform clinical assessment and review reported vital signs (oral temperature, heart rate and oxygen saturation)
- The study team will be reviewing the data reported by subject to ensure compliance, accuracy and completeness on days 1, 3, 5, 7, 9, 10, 14, 17, 21, 24, and 28.
- Once the subject meets the primary efficacy endpoint, the subject is not required to continue the self-assessment and reporting of COVID-19 symptoms. However, the study team, during the remote patient visits will evaluate and report the severity of COVID-19 associated symptoms as per the set frequency mentioned in the *Schedule of Activities*, under study staff responsibility.

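### The home-oximetry rule attaches no action to a repeat reading of 90-93%, and after Day 10 such a reading can wait 1 to 3 days for a scheduled review

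*Combined protocol and SAP*

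**What the plan says.** The oximetry rule stands in three places: section 9.2.2, section 7.1.2 and footnote 6 of the Schedule of Activities (section 2.3). All three have the same two branches.

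- **90-93%:** if the daily "result is 90-93%, the subject will repeat the measurement 2 hours later".
- **Below 90%:** "If the result is <90%, the subject is instructed to contact the study team", and the team then chooses between a 2-hour recheck and medical evaluation.

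Section 9.2.2 also asks for one further reading after 2 hours whenever saturation falls under 94%. It ties no action to the result.

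Elsewhere the protocol uses 94% as a boundary. In the synopsis (2.1), "Mild to moderate symptoms are defined as", among other things, a saturation of at least 94%. Exclusion criterion 1 in section 6.2 is "O₂ saturation <94" percent. In section 4.0, a value below 94% that is new since baseline counts as broad progression.

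On oversight, section 9.2.2 has the team review subject-reported data "to ensure compliance, accuracy and completeness on days 1, 3, 5, 7, 9, 10, 14, 17, 21, 24, and 28". It also says "Site staff to assess Adverse Event and Concomitant Medications including OTC and herbal products daily". Section 9.2.4 places the follow-up visits, "unless otherwise noted, on Day 14, 17, 21, 24, and 28". Under footnote 10, home measurement may stop after Day 10 once the subject has met the recovery endpoint.

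**The concern.** Subjects are at home and act on the rule as written. A subject who reads 92%, waits 2 hours and reads 92% again has done everything the rule asks. That repeat has the same stated consequence as a repeat of 97%: none. Yet the saturation has now been found twice below the level that would have kept the subject out of the trial.

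The stake is patient safety, and it is greatest after Day 10. Home measurement is then required only of subjects who have not yet met the recovery endpoint, and scheduled contact becomes sparse.

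**Working it through.** **Step 1. Can the existing text be read to cover a repeat of 90-93%?**

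| Reading of the rule | Consequence of a 90-93% repeat |
|---|---|
| The below-90% sentence covers only the first reading | None stated |
| The below-90% sentence also covers the repeat | None; contact still needs a value under 90% |
| The below-94% caveat in 9.2.2 applies again to the repeat | Another reading 2 hours later, with no stated end and no escalation |

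No reading leads to contact.

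**Step 2. Does another section fill the gap?**

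- Section 8.1 has the investigator reconsider management once a clinically significant finding has been identified. It does not say how a home reading reaches the investigator that day.
- Section 9.3.2 lists hypoxia and dyspnea among the adverse events to record, and 9.3.9 requires adverse events to be documented and followed. With the daily reporting and assessment in 9.2.2, this is a workable route on Days 1-10. The text is not uniform, though: the Schedule of Activities marks adverse-event assessment only on the review days.
- After Day 10, scheduled contact is the set of visits in 9.2.4, which include a review of vital signs. Nothing in the supplied text gives a same-day route between them.

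**Step 3. How long can a reading wait?** Inputs: the review days in 9.2.2 and footnote 5, which are 1, 3, 5, 7, 9, 10, 14, 17, 21, 24 and 28. Wait = next review day minus day of reading. A reading on a review day is counted as seen that day.

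Days 11-28 are 18 days, of which 5 are review days (14, 17, 21, 24, 28). That leaves 18 - 5 = 13 without review.

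| Days without review | Next review | Waits (days) | Sum |
|---|---|---|---|
| 11, 12, 13 | 14 | 3, 2, 1 | 6 |
| 15, 16 | 17 | 2, 1 | 3 |
| 18, 19, 20 | 21 | 3, 2, 1 | 6 |
| 22, 23 | 24 | 2, 1 | 3 |
| 25, 26, 27 | 28 | 3, 2, 1 | 6 |

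Total 6 + 3 + 6 + 3 + 6 = 24 days over 13 days; mean 24/13 = 1.85; range 1 to 3.

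On Days 1-10 the days without data review are 2, 4, 6 and 8, each with a wait of 1 day. If the daily adverse-event assessment is done as 9.2.2 says, that wait may be zero.

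**The case against.** The strongest reply is that the sponsor chose two tiers deliberately: recheck at 90-93%, call below 90%. The 94% boundary serves eligibility and endpoint classification. It does not by itself show that every confirmed value below 94% needs a same-day call, and the documents give no clinical standard for 90-93%. This stands in part. It makes the point a recommendation rather than an error in the plan. It does not explain why a repeat is ordered with no consequence stated if it is again 90-93%.

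Second, oversight on Days 1-10 is close: adverse events are reported and assessed daily and drug adherence is checked daily. This largely stands, so the weight of the point falls after Day 10.

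Third, instructions to subjects may sit elsewhere: in the oximeter instructions supplied with the kit (7.1.1), the Manual of Procedures named in 11.4, or the consent form. None was available. This also stands. The finding is limited to the supplied protocol text, although a threshold for calling belongs beside the below-90% threshold already there.

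Fourth, the practical value may be small. The amendment history (section 13) names version 3.0 as the last one implemented, and the documents do not say whether enrollment was open at version 5.1.

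A reader might also infer that subjects with a confirmed low reading are told not to call. The text does not say so. It is silent, and a subject remains free to call.

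**Conclusion.** The point holds as a patient-safety improvement of the lowest severity. In the supplied text a repeat of 90-93% triggers no action. After Day 10 it can wait 1 to 3 days for a scheduled review, on 13 of 18 days, in subjects who are still measuring and do not call on their own initiative. This assumes that reviews take place on the listed days and that no document outside the supplied text gives a call instruction.

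Three stronger conclusions are tempting and are not supported.

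- **A count of affected subjects.** The documents give no desaturation rate. Projecting who is still unrecovered at Day 10 from the design medians of 5 and 4 days would need a survival distribution that 10.2.2 does not state for this endpoint; it states only proportional hazards. It would also have to allow for the 4 consecutive days needed to confirm recovery. Even then it would count subjects still measuring, not subjects with low readings.
- **Bias or loss of power.** The rule is the same in both arms of a blinded trial, and nothing here changes the primary analysis.
- **An undefined endpoint.** Which of two same-day readings counts toward broad progression may be settled in SAP 3.1, which was not supplied.

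**What to change.** Put one rule in section 9.2.2, section 7.1.2 and footnote 6:

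- At 90-93%, repeat in 2 hours.
- If the repeat is still below 94% or cannot be taken, contact the study team the same day.
- Below 90%, contact the study team at once.

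Check that the subject's oximeter instructions say the same. Endpoint definitions, sample size and analyses stay as they are.

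The cost is one clause in three places, some extra calls and possibly some additional emergency visits. Emergency visits for COVID-19 worsening or shortness of breath are components of the progression endpoints, but any increase would arise under the same blinded rule in both arms. If enrollment had already closed at version 5.1, the clause helps only later use of this text.

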9.2.4 Post Treatment Days (Day 14 to Day 28)

The following procedures will be performed at all follow-up visits (post-treatment days), expected to be done remotely, unless otherwise noted, on Day 14, 17, 21, 24, and 28:

- Assess for AEs
- Review and assess COVID-19 signs and symptoms
- Document all current medications, including medications over the counter and herbal medications
- Document subject's status as an outpatient, subsequently hospitalized, or died
- Perform clinical assessment and review reported vital signs (oral temperature, heart rate and oxygen saturation)
- The study team will be reviewing the data reported by subject to ensure compliance, accuracy and completeness on days 1, 3, 5, 7, 9, 10, 14, 17, 21, 24, and 28.
- Once the subject meets the primary efficacy endpoint, the subject is not required to continue the self-assessment and reporting of COVID-19 symptoms. However, the study team, during the remote patient visits will evaluate and report the severity of COVID-19 associated symptoms as per the set frequency mentioned in the *Schedule of Activities*, under study staff responsibility.

9.2.5 Final Study Visit (Non-hospitalized Subjects) (Day 28)

The following procedures will be performed at the final post treatment visit (remote patient visit):

- Assess for AEs
- Document all current medications, including medications over the counter and herbal medications
- Document subject's status as an outpatient, subsequently hospitalized, or died
- Perform clinical assessment to evaluate for increased severity of COVID-19 related symptoms
- Pregnancy test for women of child-bearing potential

9.2.5 Early Termination/Hospitalization

All subjects have the right to withdraw from study participation at any time during the study. If, for whatever reason, a subject withdraws from the study or is hospitalized, an Early Termination Visit will be performed.

The following procedures will be performed at the Early Termination Visit:

- Assess for adverse events
- Document all current medications, including medications over the counter and herbal medications
- Perform clinical assessment (as deemed feasible if hospitalized)
- Evaluate for increased severity of COVID-19 related disease
- Pregnancy Test for women of child-bearing potential

If clinical evaluation is deemed not feasible due to subject condition, the study team to collect Early Termination Visit data and attempt to collect Day 21 and Day 28 data and AE assessment for those subjects who are hospitalized and deemed off study.

9.2.6 Safety and Other Assessments

For Study procedures and evaluations to be done as part of the study to monitor safety and support the understanding of the study intervention's safety refer to Section of Schedule of Activities and Section of Study Assessments.

9.3 Adverse Events and Serious Adverse Events

Adverse event data will be summarized for all subjects from the date of informed consent. Site-reported serious adverse events and unexpected adverse drug reactions will be summarized as subject-based counts and percentages by AE category, MedDRA system organ class and preferred term. In addition, subject listings will be provided for serious, unexpected, and unanticipated adverse reactions. Any adverse events leading to discontinuation of study drug or death will also be listed for all subjects.

9.3.1 Definition of Adverse Event (AE)

An AE is defined as any unanticipated medical occurrence regardless to relationship of the investigative arm of the trial. An AE can be any unintended sign, lab abnormality, symptom, or disease associated with the trial. Any abnormality that presents during a medical test are to be defined as an AE if it produces clinical signs and/or symptoms, requires intervention, or deemed clinically significant by the Investigator.

9.3.2 Specific AEs to record

The *Common Terminology Criteria for Adverse Events (CTCAE) version 5.0* will be utilized for AE reporting the following study- specific AEs:

- Cough
- Dyspnea
- Hypoxia
- Nausea
- Vomiting
- Abdominal pain
- Pruritus
- Loss of appetite
- Dizziness
- Skin rash

9.3.3 Definition of Serious Adverse Event (SAE)

An AE or suspected adverse reaction is considered "serious" if, in the view of the Investigator, it results in any of the following outcomes:

- Death
- A life-threatening AE
- Requires inpatient hospitalization or prolongs existing hospitalization
- persistent or significant incapacity or substantial disruption of the ability to conduct normal life functions
- Medically important event by the Investigator (including any ED visit)
- Congenital anomaly/birth defect

Important medical events that may not result in death, be life-threatening, or require hospitalization may be considered serious when, based upon appropriate medical judgment, they may jeopardize the subject and may require medical or surgical intervention to prevent one of the outcomes listed in this definition.

